### 2.3.3 ADA population

ADA population is defined as:

- All efpeglenatide participants from the safety population with at least 1 post-Baseline valid ADA sample after drug administration.

### 2.3.4 PK population

PK population is defined as:

- All participants from the safety population with at least 1 measurable serum efpeglenatide concentration available for PK analysis.

## 2.4 STATISTICAL METHODS

In general, descriptive statistics of quantitative efficacy and safety endpoints (result and change from baseline) by scheduled visit will be provided on observed cases (OC), ie, only including participants having a non-missing assessment at a specific visit.

### 2.4.1 Demographics and Baseline characteristics

Parameters described in [Section 2.1.1](#) will be summarized on the ITT population by randomized treatment group and overall using descriptive statistics.

Continuous data will be summarized using the number of available data, mean, standard deviation (SD), median, minimum, and maximum for each treatment group. Categorical and ordinal data will be summarized using the number and percentage of participants in each treatment group. Missing data will not be categorized in the summaries.

Medical history will be summarized on the ITT population by treatment group (and overall), primary SOC, and HLT, with events sorted by primary SOC in internationally agreed order and decreasing frequency of HLT in the overall group.

Technical formulas are described in [Section 2.5.1](#).

P-values on demographic and Baseline characteristic data will not be calculated.

#### **2.4.2 Prior or concomitant medications**

The prior, concomitant, and post-treatment medications will be presented for the ITT population and the following two summaries will be produced for each:

- All medications (excluding anti-diabetic), and
- Anti-diabetic medications.

Medications will be summarized by treatment group (and overall) according to the WHO-DD, considering the first digit of the ATC class (anatomic category) and the first 3 digits of the ATC class (therapeutic category). All ATC codes corresponding to a medication will be summarized, and participants will be counted once in each ATC category (anatomic or therapeutic) linked to the medication. Therefore, participants may be counted several times for the same medication.

The table for prior medications will be sorted by decreasing frequency of ATC followed by all other therapeutic classes based on the overall incidence across treatment group. In case of equal frequency regarding ATCs (anatomic or therapeutic categories), alphabetical order will be used.

The tables for concomitant and posttreatment medications will be sorted by decreasing frequency of ATC followed by all other therapeutic classes based on the incidence in the Efpeglenatide 6 mg treatment group. In case of equal frequency regarding ATCs (anatomic or therapeutic categories), alphabetical order will be used.

Similar to concomitant medications, prohibited medications will be sorted by decreasing frequency of ATC followed by all other therapeutic classes based on the incidence in the Efpeglenatide 6 mg treatment group.

#### **2.4.3 Extent of investigational medicinal product exposure and compliance**

The extent of IMP exposure and compliance will be assessed and summarized by actual treatment within the safety population ([Section 2.3.2](#)).

##### **2.4.3.1 Extent of investigational medicinal product exposure**

The extent of open-label IMP exposure will be assessed by cumulative exposure (patient years), duration (days), and category (weeks).

Duration of open-label IMP exposure is defined as last dose date – first dose date + 7, regardless of unplanned intermittent discontinuations (see [Section 2.5.3](#) for calculation in case of missing or incomplete data).

Duration of open-label IMP exposure will be summarized descriptively as a quantitative variable (number, mean, SD, median, minimum, and maximum). In addition, duration of treatment exposure will also be summarized categorically by numbers and percentages for each of the following categories and cumulatively according to these categories: 1 to 2 weeks, 3 to 4 weeks, 5 to 8 weeks, 9 to 12 weeks, 13 to 18 weeks, 19 to 24 weeks, 25 to 30 weeks, 31 to 43 weeks, 44 to 56 weeks, and >56 weeks. The duration of treatment exposure in weeks will be the duration (in days)/7, rounded to the nearest integer.

Duration of study will be summarized separately and analyzed descriptively as a quantitative variable (number, mean, SD, median, minimum, and maximum). The study duration is defined as date of completion or discontinuation – date of first open-label IMP + 1. If the date of first open-label IMP is missing, then the date of randomization will be used.

### **2.4.3.2 Compliance**

A given administration will be considered noncompliant if the participant did not take the planned dose of treatment as required by the protocol. No imputation will be made for participants with missing or incomplete data.

Percentage of compliance for a participant will be defined as the number of injections (partial injection will be counted as 1 injection) that the participant was compliant divided by the total number of injections that the participant was planned to take during the treatment period defined from the first to the last dose injection. Number of planned injections is calculated as following:

$$1 + (\text{last dose date} - \text{first dose date} + 1)/7, \text{ rounded to the nearest integer.}$$

Treatment compliance will be summarized descriptively as quantitative variables (number, mean, SD, median, minimum, and maximum). The percentage of participants whose compliance is <60%, ≥ 60% and < 80%, ≥ 80% and ≤ 100%, or > 100% will be summarized.

Cases of overdose will constitute AESIs and will be listed as such.

### **2.4.3.3 Frequency of injections**

The frequency of injections during the on-treatment period will be summarized separately by time of day (morning, afternoon, evening, night) and location of injection (Abdomen, Arm, Thigh, Other, Missing). For analysis purposes, morning is defined as the time between 06:00-11:59, afternoon as between 12:00-17:59, evening as between 18:00-23:59, and night as between 00:00-05:59.

## **2.4.4 Analyses of efficacy endpoints**

Efficacy analyses will be performed on the ITT population using efficacy assessment collected during the study, including those obtained after IMP discontinuation and/or introduction of rescue therapy, unless otherwise specified (see [Section 2.5.4](#)).

Due to COVID-19 pandemic, participants may not be able to maintain their regular clinical visits according to the study protocol, with the closure of facilities, safety concern for the participants to go to the sites, unavailability of the investigators for treating participants, interruption of transportation or other COVID-19 related reasons. Data missingness due to these reasons is likely to be missing at random. For a continuous endpoint, all observed data of participants within the same treatment group can be used for imputation in an MAR approach. Sensitivity analyses will be performed to take into consideration of the impact of COVID-19 if the number of participants with missing endpoint data due to COVID-19 is above the threshold as specified in the following sections.

#### **2.4.4.1 Analysis of primary efficacy endpoint**

##### **Hypothesis Testing of the Primary Endpoint:**

For the primary efficacy variable of change from Baseline to Week 56 in HbA1c, the following statistical null hypothesis and alternative will be tested as:

- H0: efpeglenatide - dulaglutide  $\geq$  0.3%
- H1: efpeglenatide - dulaglutide  $<$  0.3%

The null hypothesis will be tested at a 1-sided alpha level of 0.025 using a non-inferiority margin of 0.3%.

##### **Primary Analysis:**

The statistical analysis for the primary endpoint is described below.

The Baseline value is defined in [Section 2.1.1](#).

Analysis of the primary efficacy endpoint (change from Baseline to Week 56 in HbA1c) will be performed using the ITT population, using HbA1c measurements obtained during the study, including those obtained after IMP discontinuation or introduction of rescue therapy.

The primary efficacy endpoint of change in HbA1c from Baseline to Week 56 will be analyzed with missing values imputed by BOCF-like MI method for both efpeglenatide and dulaglutide groups, under the MNAR framework:

- For participants with missing HbA1c values at Week 56, the missing values will be imputed using a random draw from a normal distribution with mean equal to their Baseline HbA1c and the standard deviation equal to the pooled standard deviation calculated from the square root of the mean square error estimated from a regression model with Baseline HbA1c as the dependent variable and randomization strata and treatment as the covariates.

In this analysis, missing endpoint values will be imputed 10 000 times to generate 10 000 data sets with complete data. Each of the complete datasets after the imputation will be analyzed by the ANCOVA model with the treatment groups (efpeglenatide 4 or 6 mg, dulaglutide 1.5 mg), randomization stratum of screening HbA1c ( $<8.0$ ,  $\geq 8.0\%$ ), Visit 3 (Day 1) BMI ( $<30$  and

$\geq 30 \text{ kg/m}^2$ ), and geographical region (North America, Eastern Europe (including Hungary and Poland)) as fixed effects, and baseline HbA1c value as a covariate.

In case a baseline value needed for multiple imputations is missing, it will be imputed by the population mean at Baseline.

SAS pseudo-codes are provided in [Appendix A](#).

Results from each complete dataset will be combined to provide the adjusted mean change in HbA1c from baseline to Week 56 (regardless of treatment discontinuation or initiation of rescue therapy) for each treatment group, as well as the between-group difference (comparing each efpeglenatide group versus dulaglutide group) and the 95% CI for the difference. This will be implemented using MIANALYZE procedure in SAS. If the UB of the 2-sided 95% CI for the adjusted mean difference (efpeglenatide versus dulaglutide) in HbA1c change from baseline to Week 56 is  $\leq 0.3\%$ , the noninferiority will be declared.

If noninferiority is demonstrated on the primary endpoint for both efpeglenatide groups, ie, the UB of the 2-sided 95% CI  $\leq 0.3\%$ , the superiority of each efpeglenatide group versus dulaglutide for the primary endpoint will be tested in a hierarchical fashion, with efpeglenatide 6 mg tested first and then efpeglenatide 4 mg.

Summary statistics (for screening value, Baseline value, observed values, and observed changes from Baseline) at scheduled visits will be provided for each treatment group. The summary will include the number of observations, mean, SD, SE, minimum, median, and maximum. Graphical presentations will also be used to examine trends over time using mean values ( $\pm$ SE) and mean changes from Baseline ( $\pm$ SE) at each of the scheduled visits (using OC).

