- Initiate an evaluation and treatment of intercurrent disease (to be reported in AE/concomitant medication parts of the electronic Case Report Form [eCRF] and the medical record)

- Stress the absolute need for the participants to be compliant with treatment
- Organize a specific interview with the participants and a Registered Dietician or other qualified nutrition professional to reinforce the absolute need to be compliant with diet and lifestyle recommendations, and schedule an FPG and/or HbA1c assessment at the next visit

If none of the above-mentioned reasons can be found, or if an appropriate action fails to decrease FPG and/or HbA1c to below the threshold values, rescue medication(s) may be introduced.

If a participant needs to start rescue therapy, an unscheduled in-person visit will be scheduled to perform pre-rescue assessments (which are the same as those specified for EOT; Week 56 [Visit 14]), prior to starting the rescue medication(s).

Prescription of open-label rescue medication(s) to treat hyperglycemia will be at the discretion of the Investigator and in accordance with local standards of care and prescribing practice. With the exception of other GLP-1 RAs and DPP-4 inhibitors, any approved medication(s) can be prescribed to treat the hyperglycemia.

If a participant requires glycemic rescue, the IMP received during the randomized, open-label Treatment Period should be continued (unless the Investigator considers a change necessary for safety reasons) and the efpeglenatide dose must remain blinded until the end of the study.

All concomitant antidiabetic medications (background metformin and/or rescue therapy) will be documented in the eCRF. The cost of NIMPs not covered by health insurance will be reimbursed by the study Sponsor where permitted by local regulations.

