### 8.1 EFFICACY ASSESSMENTS

#### 8.1.1 Hemoglobin A1c

The primary efficacy endpoint and 2 secondary efficacy endpoints are assessed by measurement of HbA1c. For the eligibility and efficacy assessments of the study, HbA1c is measured at different time points during study, by a certified level I “National Glycohemoglobin Standardization Program” central laboratory ([Section 1.3](#)).

If a participant needs to receive rescue therapy (see [Section 6.1.2.2](#)), the HbA1c assessment should be performed before the introduction of rescue medication(s).

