# 1 OVERVIEW AND INVESTIGATIONAL PLAN

## 1.1 STUDY DESIGN AND RANDOMIZATION

This is a Phase 3, multicenter, 56-week, randomized, open-label for the drug (efpeglenatide and dulaglutide) and double-blind for the doses of efpeglenatide, active-controlled, 3-arm, parallel group study in participants with type 2 diabetes mellitus (T2DM) inadequately controlled with metformin.

After a Screening phase of up to 3 weeks, participants will be centrally randomized (using permuted block randomization schedule) via Interactive Response Technology (IRT) in a 1:1:1 ratio to 1 of the following 3 treatment groups:

- efpeglenatide 4 mg
- efpeglenatide 6 mg
- dulaglutide 1.5 mg

Randomization will be stratified by Screening hemoglobin A1c (HbA1c) ( $<8.0\%$ ,  $\geq 8.0\%$ ) and Visit 3 (Baseline, Day 1) body mass index (BMI) ( $<30 \text{ kg/m}^2$  and  $\geq 30 \text{ kg/m}^2$ ). Participants will receive open-label, active-controlled treatment for 56 weeks. Additional details on the study design and plan are provided in [Section 1.4](#).

Approximately 900 participants (300 participants per treatment group [details in [Section 1.3](#)] will be randomized.

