### 1.3 DETERMINATION OF SAMPLE SIZE

The sample size calculations are performed based on the primary endpoint, change in HbA1c (%) from Baseline to Week 56.

Assuming a common standard deviation of 1.1%, and the true difference between efpeglenatide and dulaglutide is zero, 300 participants per arm will ensure that the upper bound (UB) of the 2-sided 95% CI of the adjusted mean difference would not exceed 0.3% with 91% power.

Hence, there are 3 parallel dosing arms as follows:

- Efpeglenatide 4 mg, N=300
- Efpeglenatide 6 mg, N=300
- Dulaglutide 1.5 mg, N=300

[figure not shown]

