***Analysis on completers:***

For participants in ITT population who completed the 56-week treatment period and did not start any rescue therapy before the end of the period, the primary endpoint will be assessed too by the same ANCOVA model as used for the primary analysis using the observed values.

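### The Week 56 noninferiority result has no adequate check against rescue therapy: the only planned rescue-free analysis leaves out the rescued participants

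*SAP*

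**What the plan says.** **Rescue.** Under Protocol Table 3, rescue may be triggered by HbA1c of 8.5% or more after Week 12 and of 8.0% or more after Week 30, as well as by FPG. IMP normally continues after rescue. Section 6.1.2.2 provides that "an unscheduled in-person visit will be scheduled to perform pre-rescue assessments", and section 8.1.1 requires an HbA1c measurement before rescue starts.

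**Primary analysis.** SAP 2.4.4.1 analyses Week 56 HbA1c "using HbA1c measurements obtained during the study, including those obtained after IMP discontinuation or introduction of rescue therapy". SAP 2.4.4 and 2.5.4 repeat this rule.

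**Other Week 56 analyses in SAP 2.4.4.1:**
- The tipping-point penalty applies only to efpeglenatide participants without a Week 56 HbA1c.
- The retrieved-dropout and back-up imputations split on IMP discontinuation, or not at all. Neither separates rescued participants.
- The COVID-19 analysis (2.4.4.1.1) changes only how missing values are imputed.
- The completers analysis is limited to participants who "completed the 56-week treatment period and did not start any rescue therapy before the end of the period".

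**Related outputs.** Week 30 HbA1c is analysed with the same ANCOVA and imputation (2.4.4.4.2). Rescue use is summarised by Weeks 30 and 56 (2.4.4.4.6), and time to rescue is shown by Kaplan-Meier curves (2.4.4.4.7). SAP version 2 removed the Cox model for time to rescue.

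**Two narrow exceptions.** A pre-rescue value can stand in for Week 56 if no Week 56 value exists and it falls within 30 days of Day 392 (2.5.4). A rescued participant with no usable Week 56 value is imputed around baseline.

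**The concern.** Rescue depends on the variable being tested. An arm that lowers HbA1c less will tend to have more participants above the threshold, and rescue drugs then lower their Week 56 values. The observed difference shrinks. For a superiority test that is conservative. For a noninferiority test it works in favour of the claim.

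A treatment-policy noninferiority result therefore needs a companion analysis that asks how the drugs compare without the added medication. The completers analysis cannot do this, because it conditions on not having failed. If the weaker arm loses more of its poor responders, what remains looks more alike than the randomised groups were. Agreement between the primary and completers analyses could then be false reassurance. Meanwhile the pre-rescue HbA1c, collected at an extra visit, is hardly used at Week 56.

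**Working it through.** **Inputs from the documents.** One-sided alpha 0.025 and margin 0.3% (SAP 2.4.4.1). The sample size rests on "Assuming a common standard deviation of 1.1%, and the true difference between efpeglenatide and dulaglutide is zero, 300 participants per arm", so that the upper bound "would not exceed 0.3% with 91% power" (SAP 1.3). Allocation is equal across the three arms (SAP 1.1).

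**Step 1: the plan's own figure.** SE = 1.1 × √(2/300) = 0.0898. Power at zero difference = Φ(0.3/0.0898 − 1.96) = 91.6%, against a stated 91%. The figure reproduces. Noninferiority is declared when the observed difference is at most 0.3 − 1.96 × 0.0898 = 0.124.

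**Step 2: dilution.** If rescue has the same mean effect in both arms, then

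observed difference = no-rescue difference − (excess rescue proportion on efpeglenatide × HbA1c effect of rescue).

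With the no-rescue difference set at 0.3, P(noninferiority) = Φ(dilution/SE − 1.96). The excess and the effect are assumptions, since the documents give neither.

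| Excess rescue | Effect 0.5 | Effect 1.0 | Effect 1.5 |
|---|---|---|---|
| 0 points | 2.5% | 2.5% | 2.5% |
| 5 points | 4.6% | 8.0% | 13.0% |
| 10 points | 8.0% | 19.9% | 38.6% |
| 20 points | 19.9% | 60.5% | 91.6% |

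A dilution of 0.05 (5 points × 1.0, or 10 points × 0.5) gives 8.0%. A dilution of 0.10 gives 19.9%.

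**Step 3: effect of a smaller analysis set.** The SAP moves efficacy to the mITT set after early termination (2.3.1.2), which can only be smaller. For a dilution of 0.05, illustrative sizes of 300, 200 and 150 per arm give 8.0%, 6.6% and 5.9%.

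**Step 4: direction of the completers analysis.** ANCOVA simulation, 3000 trials in each of 12 settings, no-rescue difference 0.3. Assumed: baseline mean 8.1 and SD 0.8, kept within 7 to 10; SD of change 1.1; dulaglutide change −1.0 or −1.5; 30%, 60% or 100% of those at 8.0% or more rescued; rescue effect 0.5 or 1.0. Three of the settings:

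| Dulaglutide change; share rescued; effect | Rescue, efpeglenatide v dulaglutide | Treatment policy: difference, P(NI) | Rescued excluded: difference, P(NI) |
|---|---|---|---|
| −1.5; 30%; 0.5 | 4.9% v 3.1% | 0.292, 3.0% | 0.279, 4.4% |
| −1.0; 60%; 1.0 | 17.8% v 12.6% | 0.245, 10.7% | 0.242, 10.5% |
| −1.0; 100%; 1.0 | 29.8% v 21.1% | 0.212, 26.8% | 0.167, 43.5% |

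Over all 12 settings, treatment policy declared noninferiority in 3.0% to 26.8% of trials. Excluding rescued participants did so in 4.4% to 43.5%, and gave the higher figure in 10 of the 12. Using each rescued participant's value without the rescue effect gave 2.3% to 2.9%.

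That last range is a benchmark only. The simulation has a single time point, so the pre-rescue value equals the no-rescue outcome by construction. It does not show that the imputation proposed below would do as well.

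**The case against.** **These are not false-positive rates of the planned test.** A reader might infer that the error rate rises from 2.5% to 8% or 20%. The documents do not support that. SAP 2.4.4.1 defines its target regardless of treatment discontinuation or rescue. If rescue brings that difference down to 0.25, it lies inside the margin and declaring noninferiority is correct for the stated hypothesis. This objection stands in full: the percentages are measured against a different quantity, the no-rescue difference.

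**The trial is not blind to the issue.** The adjusted Week 30 comparison falls largely before the 8.0% trigger applies, and the arm-wise rescue summaries would show an imbalance. This stands in part. Some rescue before Week 30 is possible, the Week 30 analysis is exploratory with no noninferiority test, and the summaries do not adjust the Week 56 conclusion.

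**The size is assumed.** Rescue requires a central retest and a search for other explanations, and is then optional. Investigators see post-baseline HbA1c only through alerts. With rare or balanced rescue little happens. This stands, although open-label treatment does not prevent unequal rescue.

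**The remedy has limits.** The Appendix A code has no place for an unscheduled pre-rescue value. If nearly everyone above threshold is rescued, few comparable unrescued participants remain to inform the imputation. Both points stand and shape the fix.

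**Conclusion.** The concern holds as a gap in supporting analyses, not as a fault in the primary one. No planned Week 56 analysis gives a credible noninferiority comparison without rescue, and the one that comes closest deletes the rescued participants and errs in the same direction.

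The size cannot be fixed from the documents. At a no-rescue difference of 0.3, SD 1.1 and 300 per arm, the chance of declaring noninferiority is 2.5% with balanced rescue, about 8% with 0.05 dilution and about 20% with 0.10, and somewhat lower in a smaller mITT set. This assumes the less effective arm is rescued more, with equal rescue effects across arms.

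A reader might also infer that the trial cannot tell whether noninferiority comes from efpeglenatide or from added drugs. That goes too far, because the Week 30 analysis and the rescue summaries bear on the question. They do not settle it at Week 56.

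**What to change.** Keep the treatment-policy analysis as primary. Add one supplementary noninferiority analysis to SAP 2.4.4.1, in the same analysis set as the primary (the mITT set under 2.3.1.2):

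1. In all three arms, set HbA1c after first rescue to missing.
2. Assign the pre-rescue value to the nearest scheduled HbA1c visit (Week 12, 30, 43 or 56). State which value is used if that visit already holds one.
3. Impute within arm with the MCMC and monotone regression steps of 2.4.4.1.1, then apply the same ANCOVA and 0.3% margin.
4. Because unrescued participants above threshold may be few, also report a version that takes the pre-rescue value itself as the endpoint for rescued participants.
5. Describe noninferiority as robust to rescue only if both versions agree with the primary analysis. Do not rest that statement on the completers analysis.

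**Cost.** No new data are needed. The work is a mapping rule, adapted imputation code and extra output. The interval will be wider and the imputed version relies on missing at random. All of this is confined to a supplementary analysis; the primary test and its power do not change.
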